A key issue in many settings, including ours, is that testing falls into a separate budget from the treatment of patients with CDI infections. This has the potential to distort the decision of whether to run a test and, if so, what sort of test. The distortions are of two types. First, the hospital may decide to order more tests than is optimal, since the tests are perceived as "free" from the perspective of decision-makers. At the same time, the diagnostic facility may choose low-cost, slow diagnostics, because the costs associated with delays in test results are borne by the hospital. This is a classic case of silos in health care costs inefficiently distorting policy decisions, with potentially negative results for both patient health and costs.

Many institutions follow the clinical practice guidelines provided by the Infectious Diseases Society of America for the management of *C. difficile* (Cohen et al., 2010). As part of routine Infection Prevention and Control (IPC) management, patients with acute diarrhea of unknown cause are pre-emptively placed in private rooms with additional contact precautions, which mandate the use of gowns and gloves for healthcare workers. This is also known as patient isolation. Investigation for gastrointestinal pathogens is typically initiated and the duration of patient isolation depends largely on the result of microbiological testing. When severe or complicated CDI is suspected, patients are initiated on empiric treatment as soon as the diagnosis is suspected. Generally, oral metronidazole is used for mild-to-moderate CDI and oral vancomycin for severe CDI. Among hospitalized patients with acute diarrhea, initiation of pre-emptive management for CDI is common. With requested CDI screening, 85% are negative on GDG screen and 89% are negative post PCR confirmation.

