This study is a cross-sectional CRXO in that, each cluster-period consists of different individuals (patients). The order in which the interventions are delivered to each cluster (ward) is randomized to control for potential period effects. Within Foothills Hospital there are 40 wards which will be observed over a 12-month period. Each ward is randomly assigned to administer one of the two interventions for the first 6-month period (Period 1). In the second 6-month period (Period 2), the ward will administer the other intervention. Within each ward (cluster) there are two cluster-periods. Study outcomes during Period 1 and Period 2 intervention will be compared in both arms (NPT and centralized laboratory testing).

NPT testing can deliver results within several hours, while typically off-site testing takes one to two days. If NPT and the off-site testing deliver identical test results as our pilot data suggest, we can follow the clinical outcomes for each arm without the confounder of differences in test performance. As a contingency, if variation in test performance characteristics is found, analysis of patient outcomes will take this into consideration.

For patients without CDI, the antibiotics, and in many cases, the isolation, are unnecessary. NPT testing has the potential to avoid this unnecessary use of antibiotics and to avoid costly isolation procedures for the day+ that standard testing requires. It also enables a better-directed diagnostic process for the cause of diarrhea. For patients who are positive for CDI, the earlier test result will influence downstream events such as initiation of antibiotic therapy, resolution of disease, hospitalization days, and other clinical outcomes.

We hypothesize that NPT for CDI will result in reduced patient isolation days in the hospital, decreased morbidity and mortality, reduced unnecessary antibiotic use and overall reduced costs to the health care system, including both hospital and laboratory.

Previous data has indicated that the mean number of patients a ward is 39/month ($SD=43$) for a total of 1578 patients in a 6-month period and the mean number of negative patients is 33/month ($SD=34$) for a total of 1300 negative pts in a 6-month period. The inclusion criteria will be diarrhea in adult patients admitted to four acute care hospitals in the Calgary region being tested for CDI. Outpatients and patients in the emergency room will be excluded.

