Our primary endpoint is to examine the differential effect of NPT on the duration of contact precautions (i.e. patient isolation days). Secondary outcomes will compare turn-around times from specimen submission to result, days of hospitalization, the number of days of antibiotic therapy, the incidence of CDI, severe CDI, and in-hospital mortality. A comprehensive economic evaluation will be performed to determine the cost of testing, patient isolation, and hospitalization for all patients in the control and treatment arms.

Methods:

Contact precautions (i.e. patient isolation) due to CDI will be defined as an order by healthcare workers for contact precautions within the 7-day infection window of a CDI diagnosis. The length of time on contact precautions will be defined as the calendar date contact precautions are completed or patient discharge date minus the calendar date contact precautions are ordered. Data on contact precautions will be extracted from the clinical patient management system in Calgary, known as Sunrise Clinical Manager (SCM). It is used extensively in all Calgary acute care facilities and emergency departments. These data include patient identifiers (e.g. patient health number, names, date of birth), start and stop dates of isolation, facility, and patient care unit where isolation order was placed, and reason for isolation (e.g. CDI, diarrhea). These data will be linked to the specimen results tested for CDI by the patient's Personal Health Number (PHN). Turn-around times from specimen submission to result will be provided by Calgary Laboratory Services. Days of hospitalization will be defined as the difference between the admission and discharge date. The specimen results will be linked to the Discharge Abstract Database using the patient's PHN to determine during which acute care encounter the specimen was collected and the admission/discharge dates of that encounter. Antibiotic therapy will be defined as the administration of antibiotics initiated on the day of and up to 48 hours after specimen collection for CDI testing. Total days of antibiotic therapy during the acute care encounter will be defined as the calendar date antibiotic therapy is completed minus the calendar date antibiotic therapy is ordered. The data will be extracted from SCM.

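### The antibiotic-days outcome does not separate CDI-directed therapy from other antibiotics started around the test, although the hypothesis concerns only the former

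*Combined protocol and SAP*

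**What the plan says.** **The hypothesis (Study Objectives).** NPT is expected to bring "reduced unnecessary antibiotic use and overall reduced costs to the health care system". The reasoning is given just before: "NPT testing has the potential to avoid this unnecessary use of antibiotics". The premise for this, in the protocol's words, is: "For patients without CDI, the antibiotics, and in many cases, the isolation, are unnecessary". Background and Significance describes the pre-emptive treatment in question and says that, generally, "oral metronidazole is used for mild-to-moderate CDI and oral vancomycin for severe CDI".

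**The outcome (Study Objectives and Methods).** The secondary outcomes include "the number of days of antibiotic therapy, the incidence of CDI, severe CDI, and in-hospital mortality". Methods gives the rule: "Antibiotic therapy will be defined as the administration of antibiotics". Only courses that start between the collection day and 48 hours later qualify. Duration follows: "Total days of antibiotic therapy during the acute care encounter will be defined as the calendar date antibiotic therapy is completed minus the calendar date". The date subtracted is that of the order. The data come from SCM. No agent, route or indication is named.

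**The analysis (Data Analysis).** The example regression has CDI status and severity among its patient covariates and allows the NPT indicator to be interacted with other variables. It has no term for drug or indication.

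**The concern.** A negative CDI result makes pre-emptive CDI treatment unnecessary. It does not by itself make an antibiotic started for another infection unnecessary. Followed literally, the rule in Methods adds both together, and a course for another infection that starts inside the window counts to its end.

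The plan avoids this for isolation: Methods ties contact precautions to CDI and extracts the reason for the isolation order. The antibiotic outcome has no such restriction.

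What is at stake is interpretation. A null result on all-antibiotic days could mean that NPT does not reduce unnecessary CDI treatment, or that a real reduction was lost in variation from other therapy. The outcome as defined cannot tell these apart, in a trial that presents itself as evidence on rapid testing and antibiotic stewardship.

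**Working it through.** **No figure to reproduce.** The documents give no SD, effect size, power or share of patients treated empirically for this outcome. The check is therefore a comparison of texts, followed by an illustration on assumed inputs.

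**1. Hypothesis against definition.**

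| Element | Hypothesis | Outcome as defined |
|---|---|---|
| Drugs | Pre-emptive CDI treatment | Any antibiotic |
| Route | Oral, for the agents named in Background | Any |
| Patients | Those without CDI | All tested; negatives separable through the model |
| Timing | While the result is awaited | Started from collection day to 48 hours after, then the full course |

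The timing and patient rows are partly handled by the window and by the CDI-status covariate. The drug and route rows are not handled anywhere.

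**2. General formula.** Write all-antibiotic days A = C + O, where C is CDI-directed days and O is other-antibiotic days. Assume that O is independent of C, is unaffected by NPT and has SD r times that of C. The expected difference between arms is then unchanged, and

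SE(A) / SE(C) = sqrt(1 + r^2).

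| r (assumed) | SE multiplier |
|---|---|
| 1 | 1.41 |
| 2 | 2.24 |
| 3 | 3.16 |
| 5 | 5.10 |

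**3. One worked scenario.** The number of CDI-negative patients, 1300 per six months, is the total in Study Objectives. With crossover over two such periods this is taken as 1300 per arm. Everything else is assumed:
- 20% of negatives are treated empirically, with mean 2 and SD 2 days among the treated;
- 1 day is saved per treated patient, so the difference is 0.20 × 1 = 0.20 day per negative patient;
- 30% start another antibiotic in the window, with mean 7 and SD 5 days;
- two-sided alpha is 0.05.

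Variances:
- C: 0.20 × (2² + 2²) − (0.20 × 2)² = 1.60 − 0.16 = 1.44, so SD 1.20.
- O: 0.30 × (5² + 7²) − (0.30 × 7)² = 22.20 − 4.41 = 17.79, so SD 4.22 and r = 4.22 / 1.20 = 3.5.
- A: 1.44 + 17.79 = 19.23, so SD 4.39.
- Sample size ratio for equal power: 19.23 / 1.44 = 13.4.

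Power = Φ(0.20 / SE − 1.96), with SE = SD × sqrt(2 × design effect / 1300):

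| Design effect | CDI-directed days | All-antibiotic days |
|---|---|---|
| 1 | 99% | 21% |
| 2 | 85% | 13% |

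**4. Range.** I varied the share treated (10% to 40%), the days saved (1 to 1.5) and the share starting another antibiotic (10% to 50%, with its mean and SD varied too). The required sample size rises 2.5-fold to 41-fold. Power for all-antibiotic days runs from about 5% to nearly 100%. Dilution occurs throughout, but its size depends entirely on inputs the documents do not give.

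**The case against.** The strongest reply has four parts.

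- **The window already restricts the outcome.** It excludes courses begun before the collection day, so it removes much of the antibiotic exposure that precedes CDI. This stands. It would be wrong to infer that every antibiotic of the admission is counted. No document says how many patients start a non-CDI antibiotic inside the window. Those who do, however, still contribute the full course.
- **The definition may be shorthand for CDI treatment.** The window is anchored to the CDI specimen, so this is possible. If so, the text needs the restriction written in, because an analyst who follows it as printed would include everything.
- **The model deals with it.** In part. CDI status and its interaction with NPT can give an effect in negatives, and ward, month and patient covariates may absorb some background variance. The multipliers above are therefore unadjusted. No term separates CDI-directed drugs from other drugs within negative patients.
- **Total antibiotic days is a legitimate stewardship outcome.** Agreed. Study Objectives expects a better-targeted search for the cause of diarrhoea, so NPT might change other prescribing, and the assumption of no effect on O may fail. That is a reason to keep total days, but it does not make total days a direct test of the stated hypothesis.

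A reader might also infer that the effect is bound to be buried. The documents do not show this: with frequent empiric treatment and little other antibiotic use it would remain detectable. Nor does chance imbalance in other infections bias the comparison. It is noise that the standard error of a randomised comparison already covers.

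**Conclusion.** The point holds as a mismatch between a secondary outcome and the hypothesis it is meant to test. The direction, dilution, follows from the definition if NPT leaves other prescribing unchanged. The size cannot be established from the documents. The 1.4- to 5.1-fold multiplier and the power figures are illustrations that rest on independence, no NPT effect on other antibiotics, additive course days and assumed SDs and shares, without covariate adjustment. This is a worthwhile improvement and not a threat to the trial's main conclusion.

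**What to change.** Before the data are examined, add a definition of days of CDI-directed therapy and name it as the outcome that tests the hypothesis on unnecessary antibiotic use:

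- Identify it from SCM orders by agent and route: the oral agents named in Background and Significance, plus any others the investigators list in advance. Use indication as well where it is recorded. A drug-name filter alone is not enough, because the Background describes oral use and says only that these agents are generally used.
- Report it for all tested patients and separately for those finally CDI-negative. In positives an earlier result may bring therapy forward, which could move the count differently.
- Keep total antibiotic days, with the present window, as an additional stewardship outcome.

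The cost is small: one more secondary outcome and a prespecified order filter on the same data source. It assumes that SCM antibiotic orders carry drug and route. Methods lists the extracted fields for isolation orders but not for antibiotic orders, so this should be confirmed. Randomisation and data collection on the wards do not change.

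### Antibiotic courses started on a calendar day before specimen collection fall outside the antibiotic-days outcome, so any shortening of them by near-patient testing is not measured

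*Combined protocol and SAP*

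**What the plan says.** The Study Objectives list "the number of days of antibiotic therapy" among the secondary outcomes. The Methods define antibiotic therapy as "administration of antibiotics initiated on the day of and up to 48 hours after specimen collection for CDI testing", and its length as the "calendar date antibiotic therapy is completed minus the calendar date antibiotic therapy is ordered". The definition names no agents and has no look-back before the collection day. It does not say whether a patient without a qualifying course scores 0 days or is left out.

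On when treatment starts, the Background says of suspected severe or complicated CDI that "patients are initiated on empiric treatment as soon as the diagnosis is suspected". It adds: "Among hospitalized patients with acute diarrhea, initiation of pre-emptive management for CDI is common".

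On the expected benefit in patients without CDI, the Study Objectives say that "NPT testing has the potential to avoid this unnecessary use of antibiotics". The mechanism is turnaround: "NPT testing can deliver results within several hours, while typically off-site testing takes one to two days".

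**The concern.** For at least one group of patients, the plan ties the start of empiric treatment to clinical suspicion, while the outcome definition ties a countable start to the day of stool collection. Suspicion comes first, and a specimen can be taken only when the patient passes one. A course begun in the evening for a patient whose stool is collected after midnight is therefore not antibiotic therapy under the definition, even though it is running when the test is done. That is a course that a negative result within hours could end sooner than one that takes a day or two.

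The outcome carries the trial's hypothesis of less unnecessary antibiotic use, and it is the only listed outcome that measures antibiotic use. If part of the relevant treatment is outside the definition, a finding of no difference could mean no effect or an effect that was not measured.

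The other windows in the plan are not built this way. Severity laboratory values are taken from a 7-day window around the positive test, and isolation orders from a 7-day window for the diagnosis. Only the antibiotic window opens on the collection day.

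**Working it through.** **1. What the definition admits.** Let day 0 be the calendar day of collection.

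- Start on day 0, before or after the stool is taken: counted.
- Start after collection, up to 48 hours: counted.
- Start on day −1 or earlier, still running at collection: not counted.

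So the gap concerns earlier calendar days only. No other section brings these courses back.

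**2. Inputs.** The documents give no effect size, SD or power calculation for antibiotic days, so there is no planned figure to reproduce.

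- N = 1300 CDI-negative patients per arm. The Study Objectives give a figure "for a total of 1300 negative pts in a 6-month period". Over two periods, with each ward spending one in each arm, 2 × 1300 / 2 = 1300 per arm if the two halves are of similar volume.
- s = days saved per empirically treated negative patient: 1 to 2, assuming the quoted turnaround difference passes fully into course length.
- e = share of negative patients treated empirically: assumed, 10% to 50%.
- p = share of those courses started before the collection day: assumed, 0 to 50%.

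**3. If patients without a qualifying course score 0.** With the same s in counted and uncounted courses:

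- true saving per negative patient = e × s
- measured saving = e × s × (1 − p)
- unseen days per arm = N × e × s × p

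With e = 30% and s = 1, the true saving is 0.30 days per negative patient, or 1300 × 0.30 = 390 days.

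| p | Share of saving measured | Measured saving per negative patient | Unseen days per 1300 |
|---|---|---|---|
| 0 | 100% | 0.30 | 0 |
| 10% | 90% | 0.27 | 39 |
| 20% | 80% | 0.24 | 78 |
| 30% | 70% | 0.21 | 117 |
| 50% | 50% | 0.15 | 195 |

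For p from 10% to 50% and the full ranges of e and s, the unseen saving runs from 1300 × 0.10 × 1 × 0.10 = 13 days to 1300 × 0.50 × 2 × 0.50 = 650 days. It is zero at p = 0.

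**4. If those patients are left out.** The mean saving per counted course stays at s under the same assumption, so the (1 − p) factor does not apply. What changes is the population. With e = 30%, the contributing courses fall from 390 to 390 × 0.90 = 351 at p = 10%, or 390 × 0.70 = 273 at p = 30%, selected by when treatment began.

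**5. Effect on power, as an illustration only.** Assume 0-scoring, courses with mean 3 days and SD 2, e = 30%, s = 1 and a two-sided 0.05 test. With q = e(1 − p), the variance per negative patient is q(2² + 3²) − (3q)². With 1300 per arm and no clustering, power is 99% at p = 0 and 94% at p = 30%. With an assumed design effect of 4 it is 59% and 42%.

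**The case against.** The strongest reply is that the documents do not show that many courses are lost. The sentence on immediate treatment is limited to suspected severe or complicated CDI. The statement that pre-emptive management is common does not say that antibiotics are meant; in the same paragraph the word describes placing patients in isolation. Suspicion, test order and collection may often fall on one day, which the definition already covers. This stands: p may be close to 0.

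A second reply is that opening the window at collection is a reasonable choice. The definition covers any antibiotic, and the Background describes CDI as a consequence of antibiotic use, so a plain look-back would bring in earlier antibiotics given for other infections. This also stands against simply moving the window. It does not stand against a look-back confined to CDI-directed agents that are active at collection and were started on or after the isolation order.

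A reader might infer more than the documents support:

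- *That these patients are recorded as untreated.* The plan does not say so. The (1 − p) dilution holds only under 0-scoring.
- *That the loss differs by arm*, for instance because near-patient wards hold treatment while they wait for a quick result. Wards do know their testing method, so this is possible, but no section says it will happen. Starts before collection precede the result, and randomization should make them similar in the two arms.
- *That p can be worked out from the delay between suspicion and collection.* With starts spread evenly over the day, a delay of d hours crosses midnight in d/24 of cases, or 6/24 = 25% at 6 hours. But the documents give no delay, and the fraction applies only to courses started at suspicion, not to all empiric courses.
- *That the economic evaluation is affected.* Its listed components are testing, isolation and hospitalization. Drug cost is not among them.

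**Conclusion.** The gap in the definition is real and follows from the text: a CDI-directed course started on a calendar day before collection and still running is excluded, so any shortening of it is not measured. Its size cannot be fixed from the documents. Under 0-scoring and an equal saving in counted and uncounted courses, the outcome shows (1 − p) of the true saving: all of it if p is 0, 90% at p = 10%, 70% at p = 30%. If patients without a qualifying course are left out, the problem is selection by start timing and not dilution.

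The expected direction under 0-scoring is towards no difference, on one secondary outcome. The primary endpoint, duration of contact precautions, and the listed cost components are untouched, and a bias between the arms is not shown. The change is worth making because it is cheap and because, without it, a null antibiotic result would be hard to interpret.

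**What to change.** Amend the Methods definition before the data are extracted:

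1. Keep the present window, and also admit a CDI-directed course (the agents named in the Background) that is active at specimen collection and started on or after the linked isolation order. The test order could serve instead if its date can be extracted; the Methods do not list it among the data items, whereas isolation start dates are listed.
2. For these added courses, count days from the collection date to the stop date, so that days before collection, which the result cannot change, are not added.
3. State that a patient with no qualifying course scores 0.
4. Report by arm the share of CDI-directed courses started before the collection day. This gives p directly and shows whether it differs between arms.

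The cost is a few added clauses, a slightly wider date range in the antibiotic extract already planned from the clinical management system, and one descriptive table. A few courses given for another indication may be captured; the limits on agent and start date should keep these few. Only the measurement of a secondary outcome changes, not patient care.

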The intervention of interest is implementing a new RDT to Near Patient Testing (NPT); screening for CDI to be performed at the hospital rapid response laboratory (RRL) instead of the DSC. Techlab Inc. offers a lateral flow assay (C. DIFF QUIK CHEK COMPLETE® test) that detects both GDH and Toxin simultaneously and further simplifies the testing algorithm. As prescribed in the two-step algorithm, GDH and Toxin negatives will be reported out immediately as negative for CDI, while positive or discrepant results will be confirmed at the DSC using NAAT. The vast majority of requests for CDI testing are negative thus allowing a majority of results to be reported immediately to patient wards without NAAT confirmation at the DSC.

Study Objectives:

Calgary presents a unique opportunity to examine the effect of decentralizing CDI testing to Near Patient Testing. While it is not possible to perfectly duplicate the testing technology (described earlier) at NPT and the central laboratory, it is possible to provide equivalent testing. In a pilot study, we tested 20 stool samples by our current CLS centralized testing algorithm and anticipated NPT algorithm. Both algorithms rely on a two-step approach, namely GDH screen and molecular confirmation for toxin although the platforms are different. We had 100% concordance in the final result (presence of toxin) between the two algorithms. Further confirmation of this assumption (equivalence in performance) will be completed with a larger sample size prior to finalization of the NPT algorithm.

We will conduct a two-period, two-intervention, cluster randomized crossover (CRXO) design study at Foothills Hospital. Each cluster (ward) will receive each of the two interventions in a separate 6-month period of time leading to two “cluster-periods” with associated “wash-in” and “wash-out” periods attached. The interventions are RDT using NPT for CDI, and testing for CDI using centralized testing at the DSC.

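### The 48-hour limit on antibiotic starts closes at the upper end of the central turnaround, so result-driven courses can be missed at different rates in the two arms

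*Combined protocol and SAP*

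**What the plan says.** Antibiotic use is a named secondary outcome. The list at the end of Study Objectives includes "the number of days of antibiotic therapy, the incidence of CDI, severe CDI, and in-hospital mortality", and the hypothesis in that section expects "reduced unnecessary antibiotic use and overall reduced costs to the health care system".

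Methods defines antibiotic therapy as antibiotics "initiated on the day of and up to 48 hours after specimen collection for CDI testing". The next sentence gives the duration: "Total days of antibiotic therapy during the acute care encounter will be defined as the calendar date antibiotic therapy is completed minus" the date it was ordered.

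On timing, Study Objectives says: "NPT testing can deliver results within several hours, while typically off-site testing takes one to two days". It adds that in positive patients "the earlier test result will influence downstream events such as initiation of antibiotic therapy". Methods starts the turnaround clock at submission, not collection: "Turn-around times from specimen submission to result will be provided by Calgary Laboratory Services".

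On NPT positives, the intervention paragraph of Background and Significance reports negatives at once, "while positive or discrepant results will be confirmed at the DSC using NAAT". The diagnostic-methods paragraph of the same section describes a two-step algorithm in which only GDH-positive, toxin-negative specimens need NAAT.

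The plan gives no second window, no window tied to the result, and no separation of empiric from result-driven starts.

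**The concern.** Whether a course is counted depends on when it starts. For a course prompted by a result, the start depends on when the result arrives, and that is what the two arms change. The protocol itself expects NPT to shift initiation in positives. A fixed cut-off near the end of the central turnaround can therefore drop a different share of courses in each arm even if the same patients are eventually treated for equally long.

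The regression in Data Analysis cannot repair this, because an uncounted course never enters the outcome variable. Part of any arm difference in antibiotic days could then reflect the counting rule and not care. If mainly central courses are lost, the central mean is too low and the expected NPT reduction is masked. If mainly NPT courses are lost, a reduction could appear that is not real.

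**Working it through.** The documents give no effect size, SD or power for antibiotic days, so there is no planned figure to reproduce. The check is a timing overlap.

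**Inputs from the documents**
- Capture limit: 48 h from collection (Methods).
- Central result: 24 to 48 h (Study Objectives), clock from submission (Methods).
- Share positive: 100% - 89% = 11% (Background and Significance, after PCR), or 1 - 1300/1578 = 17.6% (Study Objectives).

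**Assumed inputs**
- All times uniform over their range.
- Collection to submission 0 to 6 h; result to first dose 1 to 8 h. Minimal-lag case: no submission lag, 1 to 4 h to dose.
- Local NPT screening 3 to 8 h.
- A 10-day course; half to all starts in positives result-driven; a missed course counted as zero days.

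**Exact 48-hour cut.** Let L be the total lag added to a central result that is uniform on 24 to 48 h. While L stays below 24 h, the share of starts after hour 48 is E[L]/24.
- No lag: 0/24 = 0%.
- Minimal lags: 2.5/24 = 10%.
- Main lags: (3 + 4.5)/24 = 7.5/24 = 31%.
- NPT, local result acted on: latest start 8 + 6 + 8 = 22 h, so 0%.
- NPT, local screening followed by the full central time: (5.5 + 7.5)/24 = 13/24 = 54%.

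**Calendar-day cut.** Suppose the limit means collection day through day 2, with collection time uniform over the day (assumed). The share missed is then E[L²]/(2 × 24²) = E[L²]/1152.
- Minimal lags: E[L²] = 0.75 + 2.5² = 7.0, giving 0.6%.
- Main lags: E[L²] = 3 + 4.08 + 7.5² = 63.3, giving 5.5%.
- NPT waiting as above: E[L²] = 3 + 4.08 + 2.08 + 13² = 178.2, giving 15.5%.

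A simulation with the same inputs returned the same shares for both cuts.

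**Days per tested patient.** Difference = (central share missed - NPT share missed) × share positive × share result-driven × 10 days. A positive value means the central arm is undercounted more.

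| Scenario (17.6% positive, all starts result-driven) | Exact 48 h | Calendar day |
|---|---|---|
| No lag | 0 | 0 |
| Main lags, wards act on local NPT result | 0.3125 × 0.176 × 10 = +0.55 | 0.055 × 0.176 × 10 = +0.10 |
| Main lags, NPT waits, screening added to full central time | -0.229 × 0.176 × 10 = -0.40 | (0.055 - 0.155) × 0.176 × 10 = -0.18 |

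With half the starts result-driven and 11% positive, the exact-cut figures shrink to 0.3125 × 0.11 × 10 × 0.5 = +0.17 and -0.229 × 0.11 × 10 × 0.5 = -0.13. The minimal-lag case with local action gives 0.10 × 0.11 × 10 × 0.5 = +0.055.

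**The case against.** The strongest reply is that the documents alone imply no loss: a result at one to two days arrives within 48 hours, and every lost course comes from an assumed lag. That stands as a limit on the size. It does not remove the mechanism, because the window runs from collection while turnaround runs from submission, and some time must pass between a result and a dose.

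Other replies that stand in part:
- Methods mixes hours with calendar dates. A calendar-day reading cuts the central loss from 31% to about 5%.
- Background and Significance calls pre-emptive management common, so the all-result-driven end is extreme.
- The 54% figure adds local screening to the full central time, which may already include screening. If it does, NPT and central losses would be about equal when wards wait. The expectation of an earlier result in positives also argues against this scenario.
- The main hypothesis concerns unnecessary use, largely in CDI-negative patients, and a short window suits empiric starts. Data Analysis lists CDI status as a covariate and allows NPT interactions, so negatives can be examined separately. That leaves the overall comparison, and the one in positives, exposed.
- The duration sentence refers to the whole acute care encounter and might be read as covering every course. It relies on the term defined just before it, so if all courses are meant the text still needs correcting. Nor does the plan say how patients without a qualifying course enter the analysis; zero days is an inference.

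A reader might infer that central courses often fall outside the window, or that the rule produces a bias of known direction. The documents support neither: they give no lags, and they do not settle which NPT positives wait for NAAT.

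**Conclusion.** The concern holds as a weakness in the definition of one secondary outcome. The 48-hour limit makes counting depend on time to result, and nothing else in the plan corrects this. The primary endpoint is unaffected, and empiric starts near collection are captured in both arms.

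With a 10-day course and the stated lags assumed, the arm difference due to the rule runs from about -0.4 to +0.55 day per tested patient. The two ends come from opposite assumptions about how NPT positives are handled, so they must not be read as the size of a single bias. Zero lies inside the range, and the ends require every start in positives to be result-driven. The case for change is that the sign and size cannot be known from the plan, while the remedy is inexpensive.

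**What to change.** - Use one capture window in both arms, long enough to hold the slowest result plus the time to act on it: for example, starts from the day of collection through day 7 or discharge. State it in calendar days or in hours, not both.
- Report the 48-hour version alongside it.
- Report antibiotic days separately for CDI-negative and CDI-positive patients, and state how a patient with no qualifying course is scored.
- Reconcile the two paragraphs of Background and Significance on which NPT results wait for NAAT, since the direction of any differential depends on it.

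The cost is one changed date limit in the SCM extraction and a few extra tables. The downside is that Methods counts all antibiotics, so a wider window brings in unrelated courses. These should not depend on arm, but they add noise in both. Limiting the wider window to courses with a CDI indication, or to CDI-positive patients, would reduce it. The protocol's existing 7-day infection window is only a loose precedent: it is anchored to a CDI diagnosis or positive test, not to collection in every tested patient.
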